3. STUDY DESIGN

This is an open label, block randomised (10 in each block), mixed method (quantitative and qualitative) study to be conducted for a period of up to 16 weeks

Children aged between 6-16 years with asthma attending the paediatric respiratory difficult asthma clinic will be recruited into the study and randomly allocated to one of three arms using block randomisation matched for age and size of group. Children will be assigned to trial one of the following four NEMD's to be tested:

1. Block 1 (10): Smartinhaler Plus™ (Adherium, New Zealand)
 - This measures inhalation usually flow sensors and is the next generation of a currently commercially available EMD
2. Block 2a (5) : Flo-Tone (Clement Clarke, UK) plus Rafi-tone, acoustic enabled Smartphone App (clin-e-cal, UK) for children aged 6 – 11 years
 - The Flo-Tone attaches to an MDI and makes a sound when the inhaler is used correctly. Rafi-tone is a Smartphone App that detects the sound and activates a game. The game is aimed at younger children and therefore children aged 6 – 11 years will be randomised to this block.
- Block 2b (5) : Inhaler Compliance Assessment (INCA™) device (INCA, Ireland)
 - This is an audio recording device which attaches to a Diskus dry powder inhaler. Analysis of the digital audio recordings enables objective assessment of inhaler use and technique. As it can only be used with a Diskus only children ≥ 12 years will be randomised to this block
3. Block 3: Video and Remote Directly Observed treatment (rDOT)
 - Children are filmed on a Smartphone using their inhaler. The clip is then automatically uploaded via a Smartphone App (Continga, UK) and reviewed by a Clinical Nurse Specialist to ensure inhaler technique is correct.

Recruitment

30 children will be recruited into the study; 10 per block (5 per block aged 6-11 years and 5 aged 12-16 years)

Visit 1: Novel electronic monitoring device (NEMD) issued

Routine clinical care assessments will be carried out at the end of the study period as below, including asthma control test (ACT) or the childhood asthma control test (cACT), exhaled nitric oxide (FeNO) and spirometry (FEV1 and BDR) .

Patient/parent/Carer will be invited to take part in the study.

Information regarding the study and its objectives will be communicated to the Patient/parent/carer in both oral and written form using patient information leaflets.

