The focus group interviews will be used to assess the usability and acceptability of the devices

➤ Quantitative data

The amount of usable data from each device will be quantified and compared.

This will provide data on the perceived accuracy of the device.

Additionally, data on asthma control and quality of life will be assessed.

These will be analysed quantitatively statically using the Statistical Package for the Social Services (SPSS). Data will be tested for normality using visual inspection, histograms and Kolmogorov-Smirnov testing. Parametric tests will be used if the data is normally distributed. If the data is not normally distributed or there are only small numbers non parametric tests will be used or the data will be logarithmically transformed. The significance levels for all tests will be set at <0.5.

Comparative analysis of variance between 2 groups for continuous data will be performed using the student's t test for normally distributed data and the Mann Whitney U tests for non normally distributed data and for more than 2 groups the ANOVA or Kruskal Wallis respectively. A comparison of the proportions between groups will be performed using the Pearson Chi 2 tests.

The quantitative and qualitative results will be amalgamated and an evidence report prepared to assess the feasibility of each device.

An expert panel will be convened to select the most appropriate device to take forward to a larger randomised controlled trial to assess the impact of the device on adherence in children with asthma.

Data and all appropriate documentation will be stored for a minimum of 10 years after the completion of the study, including the follow-up period.

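### The plan sets the significance level for every test at <0.5, so when there is no true difference each comparison has roughly a 50% chance of a false positive

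*Combined protocol and SAP*

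**What the plan says.** Section 7 (Statistics and data analysis, under quantitative data) fixes the threshold in one sentence: "The significance levels for all tests will be set at <0.5". The next paragraph lists the tests it governs:

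- two groups: "student's t test for normally distributed data and the Mann Whitney U tests for non normally distributed data";
- three or more groups: "for more than 2 groups the ANOVA or Kruskal Wallis respectively";
- proportions: "A comparison of the proportions between groups will be performed using the Pearson Chi 2 tests".

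The material to be tested is given just before: "The amount of usable data from each device will be quantified and compared", and "Additionally, data on asthma control and quality of life will be assessed". The section then combines the quantitative and qualitative findings in an evidence report, after which "An expert panel will be convened to select the most appropriate device to take forward to a larger randomised controlled trial".

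Group sizes come from section 3: "30 children will be recruited into the study; 10 per block (5 per block aged 6-11 years and 5 aged 12-16 years". Block 2 is divided between two devices, 5 children each. No other section gives a significance level, confines 0.5 to a screening step, states whether tests are one- or two-sided, or adjusts for multiplicity.

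**The concern.** A significance level is the false-positive rate the investigators accept when there is no true difference. Set at 0.5, it labels about half of all pure-chance results significant, ten times the conventional rate.

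Two things are at stake. First, the comparison of usable data between devices feeds the panel's choice of a device, so chance differences could be put to the panel as established ones. Second, accuracy and asthma control are the listed secondary outcomes, so a published statement that a device affected asthma control could rest on noise.

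Read literally, the sentence also covers the Kolmogorov-Smirnov normality check in the same paragraph. If that check is correctly calibrated, about half of truly normal datasets would fail it, which would distort the choice between parametric and non-parametric methods.

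**Working it through.** **Inputs.** Level 0.5 and the list of tests: section 7. Groups of 10, 10 and 10, or 10, 5, 5 and 10 when the four devices are kept apart: section 3. Asthma-control measures ACT/cACT, FeNO, FEV1 and BDR: study summary and section 2. Quality-of-life questionnaires PAQLQ and PACQLQ: section 5. The comparator of 0.05 is the conventional level and is an assumption, since the document does not state it.

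**Step 1: the plan's own figure.** The only calculated number is 29 participants (theme prevalence 10%, at least 2 instances, 80% probability). With X ~ Binomial(n, 0.10), P(X ≥ 2) = 1 − 0.9^n − n × 0.1 × 0.9^(n−1). This gives 0.785 at n = 28 and 0.801 at n = 29, so 29 is reproduced. Alpha does not enter, so correcting it leaves the sample size unchanged.

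**Step 2: false-positive rate per test.** The rates come from 20,000 simulated null datasets with normal data. The chi-square rates come from exact enumeration, with true proportions of 0.3, 0.5 and 0.7.

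| Test | Groups | p < 0.5 | p < 0.05 |
|---|---|---|---|
| t test | 10 v 10 | 49.8% | 5.0% |
| t test | 5 v 5 | 49.8% | 5.3% |
| Mann-Whitney, exact | 10 v 10 | 47.6% | 4.3% |
| Mann-Whitney, exact | 5 v 5 | 42.0% | 3.4% |
| ANOVA | 3 × 10 | 49.3% | 5.1% |
| Kruskal-Wallis | 3 × 10 | 50.7% | 4.7% |
| ANOVA | 10, 5, 5, 10 | 49.3% | 5.1% |
| Kruskal-Wallis | 10, 5, 5, 10 | 51.0% | 4.3% |
| Pearson chi-square | 3 × 10 | 48-50% | 4.2-4.7% |

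The exact Mann-Whitney rates fall below 50% because the statistic is discrete.

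**Step 3: smallest observed difference called significant.** For a two-sided, two-sample t test with n per group, the threshold in SD units is t(1 − α/2; 2n − 2) × √(2/n).

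- n = 10: 0.308 at α = 0.5; 0.940 at α = 0.05.
- n = 5: 0.447 at α = 0.5; 1.458 at α = 0.05.

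**Step 4: several measures.** With k independent null tests, P(at least one false positive) = 1 − (1 − α)^k.

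- k = 4 (the four asthma-control measures): 1 − 0.5^4 = 93.8%, against 1 − 0.95^4 = 18.5%.
- k = 7 (adding PAQLQ, PACQLQ and usable data): 1 − 0.5^7 = 99.2%, against 1 − 0.95^7 = 30.2%.

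**The case against.** The strongest reply is that this is a dropped zero that no analyst would follow. The same paragraph has other slips, including the name of the software package, which fits that reading. It is the likely explanation, so the consequences above hold only if the text is applied literally. But a threshold is written down so that it is settled before results are seen, and nothing in the document corrects this one.

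The second reply is that little depends on it. The primary outcome is acceptability and usability, assessed by thematic analysis; section 7 describes the study as largely qualitative and exploratory; and the panel has no p-value rule. This stands, and it limits the harm to how the quantitative results are labelled. It does not make 0.5 a deliberate choice, because the plan still prescribes formal tests.

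The third reply concerns the size of the effect, and it also stands:

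- The 50% applies only when there is no true difference.
- The measures come from the same children and are unlikely to be independent, so 93.8% and 99.2% are probably too high.
- The plan does not enumerate its tests, so the sets of four and seven are illustrations.
- The SD thresholds are for pairwise t tests, whereas ANOVA or Kruskal-Wallis is named for more than two groups.
- A 5 v 5 contrast within block 2 would be confounded with age at any level, because the two devices go to different age groups.
- The 18.5% and 30.2% at 0.05 reflect multiplicity, which is a separate matter.

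None of these points rescues the sentence.

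**Conclusion.** The concern holds: the plan's only significance threshold is wrong as written. The core result, a null false-positive rate of about 50% for most of the named tests, follows directly from the stated level. It needs no assumption beyond literal application, and the simulated and enumerated rates of 42% to 51% bear it out. The multiplicity figures rest on independence and one test per measure. The SD thresholds rest on two-sided, two-sample t tests. The error affects every quantitative comparison, but not the qualitative primary outcome or the recruitment target. It must be corrected before analysis because it applies to all tests and the results inform the choice of device.

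**What to change.** Replace the sentence in section 7 with one stating a two-sided significance level of 0.05 for all tests, after the sponsor confirms that this is the intended value. If 0.5 was deliberate, the plan must say why and for which tests.

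Two additions are worthwhile but not needed to cure the error: report estimates with 95% confidence intervals, and label the quantitative comparisons as exploratory.

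The cost is one sentence of protocol wording. Sample size, conduct and data collection do not change. Fewer results will be called significant, which is the purpose of the change.

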APPENDIX 1. SUMMARY OF INVESTIGATIONS, TREATMENT AND ASSESSMENTS		
	24	

GLOSSARY OF ABBREVIATIONS

KEYWORDS

Electronic monitoring device (EMD)
Novel electronic monitoring device (NEMD)
Compliance
Adherence
Children
Asthma

STUDY SUMMARY

TITLE	A feasibility study to assess novel electronic monitoring devices for monitoring adherence in children with asthma
DESIGN	A mixed method (quantitative and qualitative) open label, block randomised feasibility study
AIMS	
 1. To assess the feasibility of 4 novel electronic monitoring devices in children aged 6-16 years with asthma, in terms of usability and acceptability by patients/ guardians and healthcare professionals (qualitative study) 2. To evaluate the accuracy of these devices and assess whether they impact on asthma control (quantitative study)
OUTCOME MEASURES	
Primary outcome: Acceptability and usability of devices to participants and healthcare professional at Royal Brompton and Harefield NHS foundation Trust (RBHT)
 
Secondary outcomes:
 
 1. Accuracy of the adherence data collected from the devices. 2. Effect on asthma control as measured by asthma control test (ACT) or childhood asthma control test (cACT) score; exhaled nitric oxide (FENO), spirometry (FEV1) and bronchodilator reversibility (BDR).
POPULATION	Children aged 6-16 years with asthma on inhaled corticosteroid therapy.
ELIGIBILITY	Children aged 6-16 years with a diagnosis of asthma on inhaled corticosteroids who are being treated or followed up by the paediatric respiratory difficult asthma clinic at Royal Brompton hospital.
DURATION	Up to 16 weeks

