2. STUDY OBJECTIVES

Research question: Which novel electronic monitoring device (NEMD) (measuring both inhalation & activation) is the most feasible to use as a tool for monitoring adherence in children aged 6-16 years with asthma in terms of accuracy, usability and acceptability?

Aim: To conduct a feasibility study looking at four new electronic monitoring devices to monitor adherence in children with asthma aged 6-16 years prescribed inhaled corticosteroids.

Our primary objective is to assess which novel electronic monitoring device is the most feasible to use as a tool for monitoring adherence in children with asthma, in terms of its perceived accuracy, usability and acceptability by patients/guardians and healthcare professionals by using a face to face focus group discussion meeting or one to one interviews.

For the purposes of this study feasibility is the overarching term used to assess if the devices are capable of being used in clinical practice to monitor adherence.

Accuracy of the device will be assessed by capturing usable data from the devices. Usability of the device will be assessed from the focus group or one to one interviews encompassing ease of use, time taken, problems encountered, easy to learn to use the device.

Acceptability will also be assessed from the focus group discussions or one to one interviews in terms of aesthetically pleasing, liked the device, fits in with day to day living.

Our secondary objective is to evaluate the effect on asthma control as measured by asthma control test (ACT) or childhood asthma control test (CACT) score; exhaled nitric oxide (FENO), spirometry (FEV1) and bronchodilator reversibility (BDR)

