All children will be issued with a novel electronic monitoring device which will be attached to the child's usual inhaler or require an app on their mobile phone as described above. Parents and children will be provided information and advice on the use of the novel electronic monitoring device and asked to conduct up to 16 weeks of home monitoring using their allocated NEMD on their first visit.

Information on how to contact the team in case of any problems will be related to the participant in both oral and written form.

The data will be stored electronically and downloaded at the next clinic visit.

Contact by telephone will be made at day 7-14 to ensure that the device is working and to answer any other queries then at week 6-7 to determine if the device is being used appropriately and to answer any related questions.

Week 1 - for the rDOT arm, adherence data will be downloaded to check for consistencies in inhaler technique. If inhaler technique is inaccurate, the participants will be called by the respiratory nurse specialists to advise on correct technique. This will be documented as part of the data collection.

Week 4 – All devices, adherence data will be downloaded and checked to ensure that the devices are working correctly.

Visit 2: up to 16 weeks of adherence data collection

Routine clinical care assessments will be carried out at the end of the study period as below, including asthma control test (ACT) or the childhood asthma control test (cACT), exhaled nitric oxide and spirometry (FEV1 and BDR) .

Adherence data will be downloaded at the end of the study period and stored electronically.

Visit 3: Focus group or one to one interviews

The participants and their carers will be invited to a face to face focus group interview, or a one to one interview, depending on their availability at the end of the study period. The focus group and one to one interviews will utilise a semi structured questionnaire, to provide qualitative feedback on the acceptability and usability of the devices.

A separate focus group meeting will also be conducted with the paediatric respiratory nurses who are part of the MDT to assess their views on the devices used as they routinely provided all asthma devices and are also involved in downloading data from other devices that we would use as part of routine care (smart-inhaler). They will also be consented to take part in the study

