5. ASSESSMENT AND FOLLOW-UP

No study assessments will take place until written informed consent and age appropriate assent is obtained.

Routine clinical care data will be collected at the baseline visit and at the end of the study as follows:

Routine clinical care monitoring tests

Routine clinical care test to assess	Test	Visit 1: Study entry	Visit 2: completion of study
Asthma control	ACT/cACT	√	√
Spirometry	FEV ₁ /FVC/BDR	√	√
Inflammation	FeNO	√	√
Asthma related quality of life questionnaire	PAQLQ/PACQLQ	√	√
Prescription uptake		√	√
Drug history		√	
Data downloaded from device: Routine clinical care would be to download from smartinhaler	Data downloaded from new device		√

The main difference between data collection in this study and routine clinical care monitoring is that data will be downloaded from the new devices (NEMD) in comparison to the current smartinhaler device

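### Asthma control is measured before and after in every child, but section 7 defines no analysis variable and names only between-group tests, so a change common to all devices goes untested

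*Combined protocol and SAP*

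**What the plan says.** - **Aim and objective.** The Study Summary lists as its second aim "To evaluate the accuracy of these devices and assess whether they impact on asthma control (quantitative study". Section 2 says "Our secondary objective is to evaluate the effect on asthma control as measured by asthma control test (ACT", and goes on to the childhood version (cACT), FeNO, FEV1 and bronchodilator reversibility (BDR). Quality of life is in neither list. It is scheduled in section 5, and section 7 says it will be assessed.
- **Timing.** Section 5 states "Routine clinical care data will be collected at the baseline visit and at the end of the study as follows". Its table ticks ACT/cACT, spirometry with BDR, FeNO and PAQLQ/PACQLQ at both visits.
- **Design.** Section 3 says "All children will be issued with a novel electronic monitoring device" and describes no arm without one. On numbers it says "30 children will be recruited into the study; 10 per block (5 per block aged 6-11 years and 5 aged 12-16 years".
- **Analysis.** Section 7 says "Comparative analysis of variance between 2 groups for continuous data will be performed using the student's t test for normally distributed data". It then names Mann-Whitney for two groups, ANOVA or Kruskal-Wallis for more than two, and Pearson chi-squared for proportions. A general sentence sends non-normal data or small numbers to non-parametric tests or log transformation. The plan names no change score, baseline adjustment, paired test or repeated-measures model.
- **Visit 1 text.** Under Visit 1, section 3 says "Routine clinical care assessments will be carried out at the end of the study period as below". This does not fit the Visit 1 column in section 5.

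**The concern.** The plan collects a before and an after value on every child, and every child has a device. The question about asthma control that these data can address most directly is whether control changed within children. The tests named in section 7 are all worded for independent groups, and the variable to be tested is left open.

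Two things are at stake. An analyst who follows the text has no planned estimate of change for the stated secondary objective. The choice between end value, change and adjusted value could also be made after the data are seen. In a study of 30 children, a baseline value that is already collected should have a stated use.

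**Working it through.** **1. The plan's own figure.** The only computed number is 29 participants for theme detection (10% prevalence, at least 2 instances, 80%). From P(X>=2) = 1 - 0.9^n - n(0.1)(0.9^(n-1)), n = 28 gives 0.785 and n = 29 gives 0.801. The figure reproduces. It concerns themes only; nothing comparable is given for asthma control.

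**2. Inputs.** From the documents: 30 children; devices in groups of 10, 5, 5 and 10; two visits; 15 children in each age band (5 per block in 3 blocks). Assumed, because the documents do not give them: a 0.5 SD change, Visit 1 to Visit 2 correlation r of 0.3, 0.5 or 0.7, normal data, equal SD at both visits, no dropout, and two-sided 0.05 (section 7 prints <0.5).

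**3. Devices compared (the natural reading).** Add the same shift to every child's Visit 2 value. Each device mean moves equally, so the differences between means and the within-group variances are unchanged, and so is the F statistic. The rejection rate therefore stays at its false-positive rate whatever the size of the shift. Simulation with groups of 10/5/5/10 and a shared 0.5 SD shift agrees: 0.049-0.050 on change and on end values. A pooled paired t test on the same data rejects in 0.607, 0.755 and 0.928 of trials at r = 0.3, 0.5 and 0.7.

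**4. Visits compared as two groups (not stated in the plan).** The mean change has true SE = SD x sqrt(2(1-r)/n). The unpaired test uses SD x sqrt(2/n). The ratio is 1/sqrt(1-r) = 1.20, 1.41 and 1.83.

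Paired power comes from the noncentral t with dz = 0.5/sqrt(2(1-r)) and noncentrality dz x sqrt(30) = 2.31, 2.74 and 3.54. Unpaired power is simulated. The paired half-width is 2.045 x sqrt(2(1-r)/30); the unpaired one is 2.002 x sqrt(2/30) = 0.517.

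| n = 30 | r = 0.3 | r = 0.5 | r = 0.7 |
|---|---|---|---|
| Paired power | 0.609 | 0.754 | 0.927 |
| Unpaired power | 0.477 | 0.471 | 0.469 |
| Paired 95% half-width (SD) | 0.442 | 0.373 | 0.289 |
| Unpaired half-width (SD) | 0.517 | 0.517 | 0.517 |
| Unpaired type I error | 0.021 | 0.007 | 0.001 |

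The non-parametric pair behaves alike: Mann-Whitney 0.43-0.44, signed-rank 0.58-0.92.

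**5. ACT and cACT apart.** If each is used in 15 children (the age cut-off between the instruments is assumed to follow the age bands), paired power is 0.332, 0.438 and 0.643, with half-widths of 0.655, 0.554 and 0.429 SD. The pooled result on either score is imprecise even when correctly paired.

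**6. What baseline adjustment adds between devices.** The relative variance of a device contrast is 1 on end values, 2(1-r) = 1.4, 1.0, 0.6 on change, and 1-r^2 = 0.91, 0.75, 0.51 with adjustment. At r = 0.3 a change score is worse than the end value, so adjustment is the safer choice. For a 0.5 SD difference with 10 v 10, power is 0.185 on end values and 0.188, 0.222, 0.299 adjusted. With 5 v 5 it is 0.108 and 0.104, 0.117, 0.145. The gain is negligible at low correlation, and every such comparison is weak.

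**7. Groups of 5.** The smallest two-sided exact signed-rank p is 2/2^5 = 0.0625, so a before-after test within a group of 5 cannot reach 0.05.

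**The case against.** The strongest reply is that the groups in section 7 are the devices. The research question asks which device is most feasible, and independent-group tests are the right family for comparing devices. Applied to change scores they would respect the pairing, and no between-arm test is meant to detect a shift common to all arms. This stands. It narrows the point to an undefined variable, no planned estimate of change and no stated use of baseline.

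A reader might go further and infer any of the following. The documents do not support them.

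- *The plan will lose power by treating the visits as independent groups.* No section says so. The 47% against 61-93% is conditional on that choice.
- *Ignoring the pairing produces false positives.* With positive correlation it does the reverse: type I error falls below 5%.
- *A paired test would answer whether the devices affect control.* No arm lacks a device, so the pooled change is a before-after description and cannot be attributed to the devices.
- *Quality of life is part of the secondary objective.* It is collected and assessed but is not a listed outcome.
- *Device selection is compromised.* Quantitative results do feed the evidence report, but no section makes asthma control a selection criterion.

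It is also fair to say that the general sentence on parametric and non-parametric tests does not exclude paired forms. It does not call for one either.

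**Conclusion.** The point holds in limited form. Section 7 does not define the analysis variable for measures taken twice in each child, and it names only between-group tests. Followed as written, it would leave a change common to all devices untested, by construction and whatever its size. That part needs no assumption.

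The numerical loss (SE inflated 1.20 to 1.83 times; half-width 0.52 SD against 0.44-0.29 SD) arises only if the visits were tested as two groups. It also rests on the assumed 0.5 SD change, r of 0.3-0.7, two-sided 0.05 and full retention. Withdrawal is allowed, so 30 is a ceiling.

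The weight is moderate: the outcome is secondary, the study is described as largely qualitative and exploratory, and the primary outcome is not touched. The change is worth making because it uses data already being collected.

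**What to change.** In section 7:

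1. Define the analysis variable for each asthma-control and quality-of-life measure as the within-child change from Visit 1 to Visit 2, pooled over children with both values, with a 95% CI. Use the paired t test. Where changes are non-normal or numbers are small, use the Wilcoxon signed-rank test with the Hodges-Lehmann median change and its CI, in keeping with the section's existing small-numbers rule. Analyse ACT and cACT separately and say that the result is imprecise.
2. State that this is an uncontrolled before-after change and is not interpreted as a device effect.
3. Report any between-device comparison as exploratory, adjusted for the Visit 1 value, with CIs. Note that the gain from adjustment is small at low correlation. Note also that Flo-Tone/Rafi-tone (6-11 years) and INCA are confounded with age; for INCA, section 3 says "As it can only be used with a Diskus only children ≥ 12 years will be randomised to this block". Do no testing within the groups of 5.
4. Reconcile the Visit 1 wording in section 3 with the section 5 table, because a change needs a Visit 1 value. Check the Appendix 1 row for spirometry, FeNO and the asthma control test too. It shows no clear Visit 1 tick in the text read here, but extraction from the PDF may have shifted the columns.

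The cost is wording only: section 5 already schedules these values as routine care, so no visit, test or participant is added. Device-level comparisons and the separate ACT and cACT results remain imprecise, and the text should say so.

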7. STATISTICS AND DATA ANALYSIS

Sample Size

This is largely a qualitative study, focusing on the views of the participants on the usability and acceptability aspect of the devices, though there is a component of quantitative analyses in the perceived accuracy of the device.

Qualitative studies are different from quantitative studies in that they attempt to identify themes rather than quantify results. Therefore power analyses to calculate sample size are difficult to conduct and based largely on thematic saturation (where no further themes can be found).

It has been argued that the main goal is to ensure that the sample size is small enough to manage the material and large enough to provide new and rich data (15).

Braun and Clark, 2013 offer a guide on sample size based on the size of the project (small, medium, large). They suggest that for small projects, 6-10 participants for individual

interviews, 2-4 for focus groups, 10-50 participants for individual interviews in medium projects and up to 100 or over for larger projects.

Fugard and Potts, 2015 (16), offer a tool to quantify sample sizes for thematic analyses in qualitative studies to help support choices and decision making. They feel that the concept of theoretical saturation, whereby collecting more data does not add further themes is problematic for prospective study planning. They recommend that for adjusted prevalence of 10%, 2 instances and 80%, 29 participants would be required.

Though our sample size of 30 participants, randomised into blocks of 10 per each platform roughly fits into this model, it is nonetheless subjective, as this is largely an exploratory study.

Data management

The data entry will be collected by the study investigator ([name]). The data analysis will be conducted by the study investigator ([name]) and the chief Investigator ([name]).

Additionally, an independent researcher will aid with the analysis of the themes for the qualitative aspect of the study to ensure there is no bias.

All data will be entered on a paper clinical report form (CRF) and all data entered on a database (Excel or Access) held on the secure RBH server.

Data analysis.

➤ Qualitative data

The focus group interviews will be audio recorded, transcribed and put into themes to conduct an inductive thematic analysis.

25% of the transcripts will be double coded by an independent researcher from UCL, [name], experienced in qualitative research.

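### Section 7 specifies only significance tests between arms of 5 or 10 children, with no interval or between-device difference, although a panel must choose one device

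*Combined protocol and SAP*

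**What the plan says.** Section 7 (Quantitative data) states that usable data from each device will be quantified and compared, and that asthma control and quality of life will also be assessed. The methods it then names are all tests:

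- two groups, continuous data: "student's t test for normally distributed data and the Mann Whitney U tests for non normally distributed data";
- several groups: "for more than 2 groups the ANOVA or Kruskal Wallis respectively";
- proportions: "A comparison of the proportions between groups will be performed using the Pearson Chi 2 tests";
- threshold: "The significance levels for all tests will be set at <0.5".

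No summary statistic, confidence interval, between-device difference, post-hoc procedure or multiplicity rule appears anywhere in the document.

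Section 3 recruits 30 children in blocks of 10. Block 1 and block 3 each test one device. Block 2 is split into 2a (5 children, 6-11 years) and 2b (5 children, 12 years and over), each with its own device. The Sample Size text gives no power calculation for the quantitative comparison and calls the choice of 30 subjective, "as this is largely an exploratory study".

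On use of the results, Section 7 says: "The quantitative and qualitative results will be amalgamated and an evidence report prepared to assess the feasibility of each device". An expert panel then selects one device for a larger randomised trial. No decision rule is stated.

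**The concern.** The research question in Section 2 is which device is most feasible, and accuracy, judged by usable data, is one of its three criteria. The planned tests do not answer that question. An omnibus ANOVA or Kruskal-Wallis test says at most that some device may differ, not which one or by how much. The pairwise tests give a verdict without a size.

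With 5 or 10 children per device, that verdict depends more on the chosen level and on chance than on the devices. The panel would have no planned measure of how uncertain each device's result is, or how uncertain the gap between two devices is. It could take a non-significant result as similarity, or the highest observed mean as a real advantage, and the evidence report as planned contains nothing to warn against either.

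**Working it through.** **Inputs.** Arms of 10, 5, 5 and 10 (Section 3). Tests and the printed level of <0.5 (Section 7). The document gives no SD, effect size or sidedness, so I assume two-sided tests, work in SD units, use 0.8 SD as an illustrative large difference, and show both 0.05 and 0.5.

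**The plan's own figure.** Section 7 cites 29 participants to see a theme of 10% prevalence at least twice with 80% probability. P(X≥2) = 1 − 0.9^n − n(0.1)(0.9)^(n−1). At n = 28 this is 0.785 and at n = 29 it is 0.801, so 29 reproduces. It concerns detecting themes in the whole sample and has no bearing on comparing devices.

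**Pairwise precision and power.** The 95% half-width in SD units is t(0.975, n1+n2−2) × √(1/n1+1/n2):

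- 10 v 10: 2.101 × 0.447 = 0.94
- 5 v 10: 2.160 × 0.548 = 1.18
- 5 v 5: 2.306 × 0.632 = 1.46

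Power is from the noncentral t with noncentrality 0.8 × √(n1n2/(n1+n2)), which is 1.79, 1.46 and 1.26.

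| Comparison | Half-width (SD) | Power for 0.8 SD at 0.05 | Power for 0.8 SD at 0.5 | Difference giving 80% power at 0.05 |
|---|---|---|---|---|
| 10 v 10 | 0.94 | 40% | 87% | 1.3 SD |
| 5 v 10 | 1.18 | 27% | 80% | 1.7 SD |
| 5 v 5 | 1.46 | 20% | 74% | 2.0 SD |

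At 0.5, by definition, half of the comparisons between identical devices also come out significant.

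**Omnibus test.** Four-arm ANOVA, F(3, 26), λ = Σ n(μ − mean)²/SD². If one arm of 10 is better by 0.8 SD, λ = 10(0.533)² + 20(0.267)² = 4.27, and power at 0.05 is 33%. If one arm of 5 is better, λ = 5(0.667)² + 25(0.133)² = 2.67, and power is 22%. At 0.5 these become 86% and 77%.

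**False positives over outcomes.** Take one test on each of five outcomes (usable data, ACT/cACT, FeNO, FEV1, BDR), assumed independent. The chance of at least one false positive is 1 − 0.95^5 = 23% at 0.05 and 1 − 0.5^5 = 97% at 0.5.

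**Ranking.** In 400,000 simulated sets of four normal means with n = 10, 5, 5 and 10 and identical devices, the top mean exceeds the truth by 0.40 SD on average. It belongs to one of the two 5-child arms 56% of the time (28% each). If one device is truly better by 0.5 SD, another still ranks first about 35% of the time.

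**Proportions.** Exact 95% intervals: 8/10 gives 44% to 97%; 4/5 gives 28% to 99%.

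**Medians.** With n = 5 the full range covers the median with probability 1 − 2(0.5^5) = 93.75%. A distribution-free 95% interval for a median therefore does not exist in a 5-child arm.

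**Age bands.** Each full block has 5 children aged 6-11 and 5 aged 12-16. A like-for-like comparison of 2a or 2b with block 1 or block 3 is therefore 5 v 5, with half-width 1.46 SD. Blocks 2a and 2b share no age band, so their difference cannot be separated from age.

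**The case against.** The strongest reply is that this is mainly a qualitative feasibility study. The primary outcome is acceptability and usability, assessed by interviews and focus groups; the quantitative results are secondary; and the panel sees both together. That stands, and it limits the consequence. It does not make a bare test verdict a useful summary of the secondary results.

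A reader might infer several stronger points that the documents do not support:

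- *That the plan yields no estimates.* Sections 3 and 7 both say usable data per device will be quantified, so a descriptive figure is intended. What is missing is the named statistic, its precision and the differences.
- *That the panel will read non-significance as no difference, or the top rank as real.* Nothing says how the panel will read the report. It may do so; no more can be said.
- *That the tests will miss large differences.* This assumes 5%. At the printed <0.5, power for 0.8 SD is 74-87%, and the harm moves to false positives.
- *That the larger trial will be planned on an inflated effect.* That trial is to assess impact on adherence, and nothing says its effect size will come from this study's device means.

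The analysis groups are also not settled: Section 3 speaks of three arms and of four devices. If the three blocks of 10 are compared, only the 10 v 10 row applies. But block 2 would then mix two devices, which does not answer which device to choose.

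**Conclusion.** The point holds as a cheap improvement to the secondary quantitative analysis. The only specified inferential output is significance tests between arms of 5 or 10, with no interval or between-device difference, in a study that ends in choosing one device. At an assumed two-sided 5% level, pairwise power for 0.8 SD is 20-40%, so non-significance says little. At the printed level, half of null comparisons would be significant, so significance says little. The absence of intervals matters at both levels; which error dominates depends on the level.

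The figures assume full arms, normal outcomes with a common SD, and independence for the multiple-outcome figure. Withdrawals would widen the intervals, since Section 4.4 discards a withdrawn child's data unless more than 8 weeks were collected.

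**What to change.** In Section 7, make estimation the basis of the secondary quantitative comparison:

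1. For each device and outcome, report the mean with a 95% CI, or the proportion with an exact 95% CI. Where a median is used, give the range or interquartile range in 5-child arms.
2. Report between-device differences with 95% CIs, within the 6-11 band where block 2a is involved and within the 12-and-over band where block 2b is involved. Do not present 2a v 2b as a device difference. That leaves five contrasts: block 1 v 3, and each of 2a and 2b against blocks 1 and 3.
3. Label any tests exploratory and correct the printed significance level.
4. State in the evidence report that no device is called better or equivalent on a p-value, and that the top-ranked device's estimate is likely to be optimistic.

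The cost is wording and a table shell; no extra children, visits or data are needed. The downside is visibly wide intervals: about ±0.9 SD for 10 v 10 and ±1.5 SD for the 5 v 5 within-band comparisons. Five contrasts over five outcomes also gives 25 unadjusted intervals, so they should be presented as description and not used as tests in another form.
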